5.6.1.3. Phase allocation of Adverse Events

Solicited events are always allocated to the respective Post Dose period.

Step 1: Allocation of events to the periods:

Adverse events in the SDTM database are allocated to periods based on their start date/time. If the start date/time of an event falls between (or on) the start and stop date/time of a period, the AE is attributed to that period (treatment-emergent principle).

- In case of partial start or stop dates (i.e. time and/or day and/or month and/or year missing), the events are allocated to the periods using the available partial information on start and end date; no imputation will be done. If, for instance, the AE start date only month and year are available, these

^a In case this list of terms needs to be revised, the DPS will detail the revised list.

data are compared to the month and year information of the periods. This rule may lead to multiplication of the event as a consequence of its assignment to multiple periods.

- In case of a completely missing end date, the date is imputed by the cut-off date of the analysis for participants still ongoing in the study, and by the end date of the last period for participants who discontinued or completed the trial. In case of a completely missing start date, the event is allocated to the first active treatment phase (post dose 1 period), except if the end date of the AE falls before the start of the first active treatment phase (post dose 1 period).

Step 2: Combination of events:

Overlapping/consecutive events are defined as events of the same participant with the same preferred term which have at least 1 day overlap or for which the start date of an event is 1 day after the end date of the preceding event. Overlapping/consecutive events may be combined into one AE or not, according to the following rules:

1) If overlapping/consecutive events start in one of the following periods - Screening or post dose extension (i.e. non-active periods) - followed by an AE in - post-dose period (active period) - they are allocated to their respective periods and are considered as separate events.

2) In case overlapping/consecutive events start within a single period, they are considered as one and the same AE. The individual events which contribute to this AE are retained as individual records in the ADaM database but are assigned the same onset, period, and total duration. All related attributes to the AE/phase/period should also be consistent with the new event.

3) In case overlapping/consecutive events start in both an active period followed by a non active period, they are allocated to the active period only and are considered as one and the same AE. The individual events which contribute to this AE are retained as individual records in the ADaM database but are assigned the same onset, treatment period, and total duration. All related attributes to the AE/phase/period should also be consistent with the new event.

4) In case an active period is followed by another active period, and the overlapping/consecutive events start in both periods, they are allocated to their respective period and are considered as separate AEs. The same rule applies for 2 non-active periods.

Remarks:

1. Events can only be combined into one and the same AE if their start and stop dates are known.
2. In case the completely missing end date is imputed (for period allocation), this date is also considered as a complete date.
3. Time is not considered when determining overlap of events.

5.6.1.4. Missing Data

Missing AE data will not be imputed. Participants who do not report an event will be considered as participants without an event. An AE with a missing severity or relationship will be considered as an AE reported, but will be considered as not reported for the severity or relationship. For example, an AE with missing severity will be considered as an AE reported for the analysis of any grade, but will be considered as not reported for the analysis of at least grade 3.

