8.3.2. Method of Detecting Adverse Events, Adverse Events of Special Interest, and Serious Adverse Events

Care will be taken not to introduce bias when detecting AEs, suspected AESIs, or SAEs. Openended and nonleading verbal questioning of the participant is the preferred method to inquire about AE occurrence.

Solicited Adverse Events

Solicited AEs are used to assess the reactogenicity of the study vaccine and are predefined local (at the injection site) and systemic events for which the participant is specifically questioned and which are noted by participants in their diary.

After each vaccination, participants will remain under observation at the study site for at least 1 hour for the presence of any acute reactions and solicited events.

In addition, participants (or parents/legal guardians of the minor participants) will record solicited signs and symptoms in a diary for 7 days post-vaccination. All participants will be provided with a diary and instructions on how to complete the diary (see Overview in Section 8, Study Assessments and Procedures). Diary information will be transferred to the sponsor. After review and verbal discussion of the initial diary entries with the participant, the investigator will complete his/her own assessment in the relevant sections of the eCRF. Once a solicited sign or symptom from a diary is considered to be of severity Grade 1 or above, it will be recorded as a solicited AE.

Solicited Injection Site (Local) Adverse Events

Participants will be asked to note in the diary occurrences of injection site pain/tenderness, erythema and swelling at the study vaccine injection site daily for days post-vaccination (day of vaccination and the subsequent 7 days). The extent (largest diameter) of any erythema and swelling should be measured (using the ruler supplied) and recorded daily. The case definitions for solicited injection site events can be found in the references.^{0,0}

Solicited Systemic Adverse Events

Participants will be instructed on how to record daily temperature using a thermometer provided for home use. Participants should record the temperature in the diary in the evening of the day of vaccination, and then daily for the next 7 days approximately at the same time each day. If more than one measurement is made on any given day, the highest temperature of that day will be used in the eCRF.

Fever is defined as endogenous elevation of body temperature ≥38° C, as recorded in at least one measurement.⁰

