4. POPULATIONS (ANALYSIS SETS) FOR ANALYSIS

For vaccine studies, study intervention assignment will follow the as treated principle: all analyses (including safety, immunogenicity and efficacy analyses) will be analyzed by the actually received vaccine.

Population	Description
All screened participants (ALL)	The “all screened participants” set includes all participants that were screened, regardless of whether they were enrolled and/or randomized.
All randomized participants (ALL RANDOMIZED)	The “all randomized participants” set includes all participants that were randomized to one of the treatment groups.
Full Analyses Set (FAS)	The full analysis set will include all participants with at least one vaccine administration documented.
Per Protocol Immunogenicity Set (PPI)	The per protocol immunogenicity population will include all randomized and vaccinated participants for whom immunogenicity data are available. Samples taken after a participant meets the criteria for a major protocol deviation expected to impact the immunogenicity outcomes will be excluded from the PPI analysis. In addition, samples obtained after missed vaccinations or participants with natural infection occurring after screening (if applicable) will be excluded from the analysis set. SARS-CoV-2 infection is defined as a positive PCR test or positive N-serology.

Two additional analysis sets are defined in Appendix 2 : PPI modified and FAS modified.

The safety and COVID-19 cases analyses will be censored at the date of unblinding or the receipt of an unscheduled vaccine^a, whichever event occurs first. AEs and COVID episodes reported after unblinding or receipt of an unscheduled vaccine, whichever comes first, will be listed.

The immunogenicity analyses will be censored at the date of the receipt of

- an unscheduled vaccine,
- another live vaccine,
- unknown vaccine which is received in the window of +/-29 days at each dosing,
- other not live vaccine which is received in the window of +/-15 days at each dosing.

Immunogenicity samples excluded for the above reasons will be included in the listings and flagged.

^a Unscheduled vaccine: an authorized/licensed COVID-19 vaccine offered outside of the study.

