5.3. Primary Endpoint(s) Analysis

The primary endpoints in this study, are:

Adults

Humoral Immune Response

All participants in groups 1-3 (3 dose levels of Ad26.COVS.S administered as a 2-dose schedule at a 56-day interval):

- Serological response to vaccination as measured by virus neutralization assay (VNA) titers and enzyme-linked immunosorbent assay (S-ELISA EU/mL), 28 days after Vaccination 2.
- Antibody geometric mean titers (GMTs) (VNA) and geometric mean concentrations (GMCs) (S-ELISA), 28 days after Vaccination 2.

All participants in groups 4-5 (2 dose levels of Ad26.COVS.S administered as a single vaccination):

- Serological response to vaccination as measured by VNA titers and ELISA (S-ELISA EU/mL), 28 days after Vaccination 1.
- Antibody GMTs (VNA) and GMCs (S-ELISA), 28 days after Vaccination 1.

All participants in groups 7-9 (5×10^{10} vp dose level, administered as a 2-dose schedule at a 28-day and at an 84-day interval):

- Serological response to vaccination as measured by VNA titers and ELISA (S-ELISA EU/mL), 28 days after Vaccination 2.
- Antibody GMTs (VNA) and GMCs (S-ELISA), 28 days after Vaccination 2.

Safety and reactogenicity of Ad26.COVS.S

- Solicited local and systemic AEs for 7 days after each vaccination.
- Unsolicited AEs for 28 days after each vaccination.
- Serious adverse events (SAEs) and adverse events of special interest (AESIs) throughout the study (from first vaccination until end of the study)

Adolescents

Safety and reactogenicity of Ad26.COVS.S

- Solicited local and systemic AEs for 7 days after vaccination.
- Unsolicited AEs for 28 days after vaccination.
- SAEs (incl. Multisystem Inflammatory Syndrome in Children [MIS-C]) and AESIs throughout the study (from first vaccination until end of the study).

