Safety analyses will be performed on the FAS. Continuous variables will be summarized using the following statistics, as appropriate: number of observations, arithmetic mean (mean), standard deviation (SD), standard error (SE), median, quartiles (Q1 and Q3), minimum and maximum. Frequencies and percentages (one decimal place) will be generated for categorical variables. No formal comparisons between groups will be provided.

Safety data will be analyzed by study intervention regimens as designed per protocol^a. In addition, safety data will be analyzed by intervention regimens as designed per protocol and age group. Data will be presented by period (post Dose 1, post Dose 2, post Antigen Presentation, as applicable) as well as over the entire primary regimen, and over the entire Antigen Presentation regimen. Denominator for the percentages is the number of participants in the considered population and phase for a certain regimen (incidence per 100 participants/phase).

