5.6.1. Adverse Events

5.6.1.1. Definitions

Solicited AEs shown in the tables are extracted from the investigator assessment pages (CE) of the CRF. For unsolicited AEs, only the AEs within the 28-day period following each vaccination will be presented in the safety tables except for SAEs, which will be captured and tabulated in the outputs covering the whole study period. All other collected unsolicited adverse events will be presented through listings.

Solicited administration site symptoms will be considered as related to the study vaccine (by definition).

The severity of the AEs will be classified as grade 1 to 4. Solicited events that are graded less than grade 1, are not considered as AE. In case no grades are available, the grading of the solicited events will occur according to the grading list in Appendix 3.

For AESI, the following is defined:

- Suspected AESI : as reported by investigator and presented by: Embolic and thrombotic events (SMQ) + PT; Haematopoietic thrombocytopenias (SMQ) (broad) or HLT Thrombocytopenias + PT; Other SMQ + PT.
- Suspected AESI: Embolic and thrombotic events (SMQ), Haematopoietic thrombocytopenias (SMQ) (broad) or HLT Thrombocytopenias and presented by: Embolic and thrombotic events (SMQ) + sub-SMQ1 + PT; Haematopoietic thrombocytopenias (SMQ) (broad) or HLT Thrombocytopenias + PT;
- Qualified for assessment AESI: [Embolic and thrombotic events (SMQ)] and [Haematopoietic thrombocytopenias (SMQ) (broad) or HLT Thrombocytopenias or platelet count below normal ranges per local or central laboratory report or platelet count < 150 × 10⁹/L] and presented by: Embolic and thrombotic events (SMQ) + sub-SMQ1 + PT;

^a As indicated previously, all analyses, including the safety analyses, will be conducted by actually received vaccine (“as treated” principle). The sentence “by study intervention regimens as designed per protocol” indicates that the statistical tables are designed with the planned vaccine regimens as columns. Therefore, participants who receive e.g. “Placebo, Placebo” instead of “Ad26.COV2.S 5x10¹⁰ vp, Placebo” will appear in the “Placebo, Placebo” column. However, to avoid sparse columns, participants who receive e.g. “Placebo, Ad26.COV2.S 5x10¹⁰ vp” (which is not a planned vaccine regimen) will be excluded from the statistical tables. They will be included in the listings, as well as in the programmed patient narratives where they will appear as “Subjects with vaccine misallocation”.

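### Vaccinated participants with no solicited AE data after the on-site observation are counted as event-free, which lowers the reported reactogenicity rates whenever such data are missing

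*SAP*

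**What the plan says.** Three SAP provisions act together.

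- **Missing data (SAP 5.6.1.4).** "Missing AE data will not be imputed", followed by "Participants who do not report an event will be considered as participants without an event". Solicited and unsolicited AEs are not separated.
- **Denominator (SAP 5.6).** "Safety analyses will be performed on the FAS", and "Denominator for the percentages is the number of participants in the considered population and phase for a certain regimen". Having solicited data is not a condition.
- **Population (SAP 4).** "The full analysis set will include all participants with at least one vaccine administration documented". Diary return plays no part.

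The endpoint affected is primary. SAP 5.3 lists, for adults, "Solicited local and systemic AEs for 7 days after each vaccination", and a single-vaccination version for adolescents.

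On the data source, SAP 5.6.1.1 says: "Solicited AEs shown in the tables are extracted from the investigator assessment pages (CE) of the CRF". Under Protocol 8.3.2, participants fill in a diary on the day of vaccination and the 7 days after it; once the entries have been reviewed and discussed, "the investigator will complete his/her own assessment in the relevant sections of the eCRF". Separately, site staff document solicited events at the end of the observation period of at least 1 hour (Protocol 4.1).

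Neither document limits the solicited AE denominator to participants with data, asks for a count of those without, or plans a sensitivity analysis.

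**The concern.** For unsolicited AEs and SAEs, treating silence as no event is ordinary practice, because silence and absence usually cannot be told apart. Solicited AEs are different. Each participant is asked about a fixed list of events over a fixed period, so the record can distinguish a participant who was asked and had none from one whose data were never collected. The SAP merges the two. Although it says that it does not impute, it in effect imputes a negative answer. For immune responses, by contrast, SAP 5.7.1.2 leaves missing values out.

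SAP 5.6 plans no formal comparison between groups, so the descriptive percentage is itself the result for this endpoint. The trial sets dose levels and schedules side by side. If data completeness differs between groups or injections, part of any contrast in reactogenicity would reflect completeness. These rates also inform decisions: SAP 1 gives reactogenicity at one dose level as the reason for not going to a higher one in adolescents.

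**Working it through.** **1. The plan's own safety figure.** Protocol Table 9 gives the one-sided 95% upper limit when no events are seen. The formula is 1 - 0.05^(1/N):

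- N=25: 11.29% (stated 11.3%)
- N=50: 5.82% (5.8%)
- N=75: 3.92% (3.9%)
- N=150: 1.98% (2.0%)

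The table reproduces and is not in dispute. It assumes that all N are observed. At N=75, with 71, 68 or 60 observed, the limit would be 4.1%, 4.3% or 4.9%.

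**2. Effect of the rule.** Let N be vaccinated at a dose, m the share with no solicited data after the observation hour and no recorded solicited event, and p the event rate among the rest.

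- Events counted: p × N(1-m)
- Denominator under SAP 5.6: N
- Reported rate: p(1-m)
- Shift against the rate among those with data: -pm, never upward

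**3. Numbers.** Protocol 2.3.1 cites solicited systemic AEs in 64% (18-55 years) and 36% (65 years and older) in the first-in-human study. The values of m are assumptions, because the documents give none.

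| p | m=2% | m=5% | m=10% | m=20% |
|---|---|---|---|---|
| 64% | 62.7% | 60.8% | 57.6% | 51.2% |
| 36% | 35.3% | 34.2% | 32.4% | 28.8% |

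For example, 0.64 × 0.95 = 60.8% and 0.36 × 0.90 = 32.4%. For the local AE rates cited there (58% and 27%), m=10% gives 52.2% and 24.3%.

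**4. One group of 75.** Suppose 8 have no data and 43 of the other 67 report an event.

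- SAP rule: 43/75 = 57.3%
- Participants with data: 43/67 = 64.2%
- If all 8 had an event: (43+8)/75 = 68.0%

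The SAP rule therefore reports the lowest value compatible with the data.

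**5. Active against placebo.** The reported difference is pA(1-mA) - pP(1-mP). As an illustration, take the pooled adult fatigue rates in Protocol 2.3.1, 48.3% for Ad26 vaccines and 30.7% for placebo, a difference of 17.6 points:

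- mA = mP = 10%: 43.5 - 27.6 = 15.8 points
- mA = 10%, mP = 0: 43.5 - 30.7 = 12.8 points
- mA = 0, mP = 10%: 48.3 - 27.6 = 20.7 points

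(Unrounded: 48.3 × 0.9 = 43.47 and 30.7 × 0.9 = 27.63.) The difference can shrink or grow.

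**The case against.** The strongest case on the other side has five parts.

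- **A missing diary is not automatically a missing assessment.** Tables draw on the investigator's CRF pages, and events noted during the observation hour still count. This stands. The gap concerns participants with no solicited assessment after that hour, not everyone whose diary is absent.
- **Procedures limit missingness.** A missed diary review is made up at the next visit (Protocol 8), and early attendance triggers a phone call for the remaining diary days (schedules of activities). Someone who misses a vaccination does not enter that post-dose period (SAP 5.1.2, Table 1). All true, so m may be small. But the plan does not ask for m to be shown, so a reader could not tell.
- **The shift is small against sampling error.** At N=75 and p=64% the standard error is √(0.64 × 0.36/75) = 5.5 points, about ±11 points for a 95% interval, against a shift of 3.2 points at m=5%. That is fair for a single group. Sampling error, however, has no direction, and this shift does.
- **The illustrative rates are not this trial's.** They are blinded first-dose data from another study and serve only to give scale.
- **A Data Presentation Specification could set another denominator.** SAP 1 allows for such documents, but the SAP as written sets a different rule.

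Three stronger readings are tempting, and the documents do not support them. A reader might infer that the rule always favours the vaccine. That holds for absolute rates only, because placebo rates are diluted as well. A reader might expect the worst effect in the open-label crossover injections. SAP 4 censors the safety analysis at unblinding and lists later AEs, so no diluted crossover percentage is clearly planned, although SAP 5.1.2 does define cross-vaccination periods. A reader might also take the calculated shifts as the bias in this trial. They are scenarios.

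**Conclusion.** The point holds as a defect in the stated rule. SAP 5.6.1.4, 5.6 and 4 together count vaccinated participants without solicited data as event-free in a primary endpoint, and the reported absolute rate is then too low by p × m relative to participants with data. At p=64% that is 3.2 points at m=5% and 6.4 points at m=10%; at p=36% it is 1.8 and 3.6 points.

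This rests on an assumed m, which neither document gives. With complete data the bias is zero and the fix changes no percentage. Taking the rate among participants with data as the right target further assumes that data are missing at random. If those with more reactions are less likely to return data, even that rate is too low; if more likely, it is too high. Showing the number without data lets readers judge.

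This is an inexpensive improvement to a descriptive Phase 2a analysis. It does not put the study's conclusions in doubt.

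**What to change.** In SAP 5.6.1.4, separate the two kinds of AE.

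- **Solicited AEs.** Use as denominator the participants vaccinated at that dose who have a reported solicited event, or at least one diary-based or investigator (CE page) solicited assessment covering the 7-day period after the 1-hour observation. The last condition is needed: everyone vaccinated is observed on site, so a requirement of any post-vaccination assessment would exclude almost nobody.
- **Reporting.** Show the number without such data per group and dose.
- **Sensitivity analysis.** Repeat the solicited AE tables with the current FAS denominator.
- **Unsolicited AEs and SAEs.** Leave the rule unchanged.

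One limit remains: a partly completed diary satisfies the condition, so events on unrecorded days are still counted as absent.

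The cost is a revised paragraph, one extra denominator flag in the analysis data, and percentages that may be slightly less favourable. No new data collection is needed.

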5.6.2. Laboratory, Vital Signs and Physical Examination

Laboratory safety parameters, change from baseline and change from pre-dose x over time will be tabulated. Abnormalities on the changes from reference, if available, will be categorized. Abnormalities will be tabulated by visit and by worst abnormality. Patient profiles will be provided.

A listing of all laboratory values will be made, restricted to participants with at least one laboratory abnormality.

Physical examination findings will be summarized at baseline. A listing of the abnormalities will be made.

Vital signs including temperature, pulse/heart rate, respiratory rate, and blood pressure (systolic and diastolic) will be summarized over time, using descriptive statistics. Abnormalities emerging after vaccination will be tabulated by worst abnormality grade using the FDA table in appendix 3.

An abnormality (toxicity grade or abnormality based on normal ranges) will be considered as emerging in a particular period if it is worse than the baseline value. If the baseline is missing, the abnormality is always considered emerging. A shift from ‘abnormally low’ at baseline to ‘abnormally high’ post baseline (or vice versa) is also emerging. In case a laboratory test result is censored (no numeric value is available, but only a verbatim term) then a numeric value will be imputed by a value exceeding the cut-off value with one unit. (<x: subtract 1 unit from x, >x: add 1 unit to x; <3.45 is imputed with 3.44).

In case no toxicity grades are defined for a test, the abnormalities (above/below normal range) will be used. In determining toxicity grades, the following rules are applied:

- worst grades/abnormalities are determined over the whole observational period for each trial period separately, including all post-baseline measurements of that period.
- The abnormalities ‘abnormally low’ and ‘abnormally high’ are considered equally important, i.e. if a participant has as well an abnormally low as an abnormally high value post-baseline, both abnormalities are shown in the tables. (This means that the sum of the percentages can be more than 100%)
- Note: as the grading scale for some parameters in the grading table has some gaps (zones where no toxicity grade definition exists), laboratory results falling in these zones will be allocated to the adjacent worst-case grade.

- If a lab value falls within the grading as specified in the grading table but also within the local lab normal limits, the value is considered as normal.

For the grades, no distinction will be made between test results of samples obtained under fasting and under non-fasting conditions: in case limits under fasting and non-fasting conditions differ, the limits of the conditions (fasting/non-fasting) of scheduled visits as planned in the CTP will always be used, also for samples obtained under a different condition (e.g. samples of withdrawal visits).

A listing of participants with fever according to the FDA grading table will also be provided. In addition, temperature measurements (whether obtained from the diary or from on-site assessments) will be allocated to predefined temperature intervals (from 37.5° C until 40°C, in steps of half degree increments; eg <37.5, 37.5-<38, 38-<38.5, ... >40), and tabulated.

